4.7 ASSESSMENT OF VITAL SIGNS DURING THE OPERATIVE PERIOD

Intraoperative vital signs will be assessed by the Anesthesiology and Perioperative Medicine Service of the Hospital de Clínicas de Porto Alegre, always led by the same care team. Heart rate, blood pressure, and oxygen saturation will be measured and recorded before, immediately after, 1 minute after, and 5 minutes after the injection of each anesthetic. Significant changes, such as hypo or hypertension, bradycardia or tachycardia, and hypoxia, will be recorded and presented in the results.

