The removal of third molars is one of the most frequently performed procedures in dentistry, and can be carried out in a hospital setting under general anesthesia. In such cases, local anesthetics are often administered at the surgical site in addition to general anesthesia, to promote better hemostasis and postoperative analgesia. Bupivacaine is a local anesthetic commonly used in these situations. However, its known cardiotoxic and neurotoxic effects, as reported in the literature, have led to increased interest in safer alternatives, such as ropivacaine. **Objective:** to evaluate whether there is a significant difference between bupivacaine and ropivacaine in terms of postoperative analgesic efficacy, intraoperative hemostasis, and patient vital signs during the intraoperative period. **Materials and Methods:** This was a randomized, controlled, split-mouth clinical trial. The sample size was based on a similar previously published study and included 15 participants ($n = 30$). As this study also follows a split-mouth design, each of the 15 patients underwent two tooth extractions. All patients had indications for the removal of both lower third molars under general anesthesia. Surgical extractions were performed in a single session, with bupivacaine (Group A) administered at one surgical site and ropivacaine (Group B) at the other. The procedures were carried out at the Hospital de Clínicas de Porto Alegre. Vital signs were continuously monitored by the same anesthesiology team, with data collected at the time of drug injection (before and immediately after), as well as one minute and five minutes post-injection. Intraoperative bleeding was measured by calculating the volume of blood aspirated into the collection vial, from the time of incision to the final suture, at each surgical site. To minimize systemic interference from the anesthetic agents, their administration was alternated between patients. Postoperative analgesia was self-reported by the patients using a Visual Analog Scale (VAS) for each side at various postoperative time points. A descriptive analysis will be conducted on the clinical data obtained through these measurements.

Key-words: Third Molar; Anesthetics, Local; Surgery, Oral

SUMÁRIO

SUMMARY	5
1 INTRODUCTION	6
2 LITERATURE REVIEW	8
3 OBJECTIVES	10
4 METHODOLOGY	11
4.1 ETHINCAL ASPECTS	11
4.2 TYPE OF STUDY	11
4.3 LOCATION	12
4.4 SAMPLE	12
4.5 PREOPERATIVE CONDUCTS	13
4.6 SURGICAL TECHNIQUE	13

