2 LITERATURE REVIEW

2.1 RACEMIC BUPIVACAINE

Bupivacaine is a potent local anesthetic from the amide group, widely used in regional anesthesia, epidural anesthesia, spinal anesthesia, and local anesthesia. It is available in three different concentrations: 0.25%, 0.5%, and 0.75%.²¹ It is called racemic because it is an equimolar mixture of dextrorotatory and levorotatory isomers.²² Bupivacaine has a slow onset of action (6 to 10 minutes), a half-life of 2.7 hours, and intrinsic vasodilatory potential. It is commonly used in more extensive procedures that require prolonged intraoperative and postoperative anesthesia.¹¹ To reduce intraoperative bleeding, toxicity, and the required dose for anesthesia, vasoconstrictors are frequently added to bupivacaine, with epinephrine being one of the most commonly used substances.²³

Bupivacaine was first synthesized in 1957 and introduced to the market in the mid-1960s. As its use increased, so did reports of adverse effects, including toxicity to the central nervous system and cardiovascular system.²⁴ Bupivacaine is closely associated with seizures, severe bradycardia, and cardiac arrest, which are often

resistant to conventional cardiopulmonary resuscitation techniques.²⁵ These side effects are frequently linked with overdose or accidental intravascular injection.²⁶

Duo to these concerns, several studies have been conducted to better understand the cause of bupivacaine's toxicity, ultimately leading to the exploration of isomers and the development of new anesthetic agents.²⁷

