3 OBJECTIVES

3.1 GENERAL OBJECTIVE

This study aims to evaluate whether there is a significant difference between 0.5% bupivacaine with 0.2MI of epinephrine and 0.75% ropivacaine with 0.2MI of epinephrine in terms of postoperative analgesic capacity, intraoperative hemostasis and the patient's vital signs during the transoperative period.

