4.6 SURGICAL TECHNIQUE

The procedure will be performed in a hospital setting, where patients undergo a single surgery for the extraction of the lower right and lower left third molars. Throughout the perioperative period, patients will be closely monitored, with their vital signs observed by both the surgical team and anesthesiology teams. As prophylaxis, patients will receive 900mg of clindamycin intravenously at the start of the procedure. The patient will be positioned supine on a hospital stretcher and placed under general anesthesia. Extra and intraoral antisepsis will be performed using a 0.12% chlorhexidine digluconate aqueous solution, and sterile surgical drapes will be used. Following these initial steps, one of the surgical sites (as selected) will be infiltrated with either 6 mL of 0.5% racemic bupivacaine + 0.2 mL of epinephrine or 4 mL of 0.75% ropivacaine with 0.2 mL of epinephrine, with approximately 25 mg of anesthetic injected. The surgical procedure will then begin. A Neumann incision with diverticulum will be made on the distal side of the adjacent mandibular second molar, followed by mucoperiosteal detachment, osteotomy, and odontosection (if necessary). The tooth will then be luxated and extracted using levers. The surgical wound will be cleaned and sutured with single or X-shaped stitches using 4-0 polyglactin sutures. Suture removal will take place between 7 and 10 days postoperatively. Before discharge, while

still in the hospital, patients will receive intravenous administration of 2g of dipyrone every 6 hours, 40mg of tenoxicam once daily, 100mg of tramadol every 8 hours, 600mg of clindamycin every 6 hours, and 4mg of ondansetron every 8 hours.

Postoperative instructions and necessary medications will be provided to patients both verbally and in writing, according to the protocol recommended by the hospital (APPENDIX B). Suture removal will be performed in an outpatient setting at the Hospital de Clínicas de Porto Alegre between 7 and 10 days postoperatively.

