4.10 DATA ANALYSIS

A descriptive analysis will be performed on the changes in vital signs observed during the operation (if any). A direct comparison and calculation of the averages will be made between the values observed in both the postoperative analgesia evaluation and the transoperative bleeding assessment.

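### Vital signs are whole-patient measures, yet the two drugs are compared on them within one session; the second injection's readings follow the first drug, so attribution to one drug is weakened

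*Protocol*

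**What the plan says.** The general objective (Protocol 3.1) compares the two drugs "in terms of postoperative analgesic capacity, intraoperative hemostasis and the patient's vital signs during the transoperative period". The Summary states the design: "Surgical extractions were performed in a single session, with bupivacaine (Group A) administered at one surgical site and ropivacaine (Group B) at the other". Section 4.6 adds epinephrine to both solutions: "6 mL of 0.5% racemic bupivacaine + 0.2 mL of epinephrine or 4 mL of 0.75% ropivacaine with 0.2 mL of epinephrine".

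For the vital signs, section 4.7 says "Heart rate, blood pressure, and oxygen saturation will be measured and recorded", at these times: "before, immediately after, 1 minute after, and 5 minutes after the injection of each anesthetic". It also says that notable events of pressure, rate or oxygenation will be reported in the results. Section 4.10 plans this: "A descriptive analysis will be performed on the changes in vital signs observed during the operation". It does not mention injection order.

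The Summary acknowledges possible interference and gives one safeguard: "To minimize systemic interference from the anesthetic agents, their administration was alternated between patients". Section 4.4 instead describes simple randomization just before surgery and does not mention order. No section states an interval between the two injections.

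**The concern.** Split-mouth pairing works when the outcome belongs to a site, such as the blood from one socket or the pain on one side. A pulse rate or a blood pressure cannot be assigned to a side. For these outcomes the design behaves like a two-period crossover with no stated washout: the first drug is given alone, the second on top of the first.

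The stake is interpretation. The case for ropivacaine in this protocol is lower cardiac toxicity, so vital signs are where a reader will look for a difference. If readings are listed by drug without regard to order, a fall in pressure after the second injection will be credited to the second drug, although it may come partly from the first drug, from epinephrine given twice, or from surgery.

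**Working it through.** **Inputs from the protocol.** 15 patients and 30 sites (4.1, sample calculation). Readings before and 0, 1 and 5 minutes after each injection (4.7). For bupivacaine, "a half-life of 2.7 hours" (2.1). No half-life is given for ropivacaine.

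**Assumed, because not stated.** The gap between injections, taken as 20 to 60 minutes. The effect sizes in step 5 are illustrative only.

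**1. Series affected.** Each patient gives two series, so 15 × 2 = 30. One per patient follows the second injection: 15 of 30.

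**2. Sequence.** In 4.6 one site is infiltrated and surgery then starts. In 4.8 the bottle already holds fluid before the second incision. The second injection therefore probably follows the first extraction. This is an inference. If both sites were injected before any surgery, the extraction part would fall away, but the two drugs would overlap more.

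**3. Drug still present.** Fraction not yet eliminated = 2^(−t/162), with t in minutes and 2.7 h = 162 min.
- 20 min: 0.918
- 30 min: 0.880
- 60 min: 0.774

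This is simple decay that ignores absorption. It applies only to patients given bupivacaine first, about half of the 15. It measures drug, not effect on pulse or pressure.

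**4. What the fresh baseline removes.** Over the 5-minute window, 2^(−5/162) = 0.979, so about 2% of the residual bupivacaine is eliminated. On this model the residue is nearly constant and largely cancels in a change from the pre-injection reading. What does not cancel is whatever is still moving: continuing absorption, epinephrine, and the response to surgery.

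**5. Bias from what remains.** Let π be the order shift left in the change score, λA the carry-over after bupivacaine, and λB the carry-over after ropivacaine. With nAB patients given bupivacaine first and nBA given ropivacaine first, the bias in the mean difference (ropivacaine minus bupivacaine) is

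[nAB(π + λA) − nBA(π + λB)] / 15.

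| Order split (nAB : nBA) | π | λA | λB | Bias |
|---|---|---|---|---|
| 8 : 7 | 5 | 0 | 0 | (40 − 35)/15 = 0.33 |
| 10 : 5 | 5 | 0 | 0 | (50 − 25)/15 = 1.67 |
| 7.5 : 7.5 (exact balance) | 5 | 5 | 2 | (75 − 52.5)/15 = 1.5 |
| 7.5 : 7.5 (exact balance) | 5 | 2 | 5 | (52.5 − 75)/15 = −1.5 |

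Balanced order removes the common shift π. It does not remove the difference between λA and λB, and the sign depends on which is larger.

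**6. Is order balanced?** Alternation of 15 patients gives 8 : 7. If the simple randomization in 4.4 also sets order, the chance of a 10 : 5 or more uneven split is 2 × P(X ≥ 10 | 15, 0.5) = 2 × 4944/32768 = 0.30.

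**7. What is free of carry-over.** Only the first-injection series: 15 patients, about 8 v 7 by drug if order is balanced. This is a between-patient comparison.

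**The case against.** The strongest reply has three parts.

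- **A baseline already exists.** Section 4.7 requires a reading before each injection and 4.10 works with changes, so a stable residue from the first drug drops out. Step 4 supports this for bupivacaine elimination. It stands, and it rules out the stronger inference that second-injection changes cannot be attributed at all. Attribution is weakened, not lost.
- **The vital-sign analysis is only descriptive.** The averages and direct comparison in 4.10 concern pain and bleeding, so no planned test is spoiled. That is correct. But 3.1 still poses a between-drug question on vital signs, and 4.7 will report events that readers will assign to a drug.
- **Tabulation detail belongs in an analysis plan.** Partly so. The overlap, however, comes from the design and the objective, and injection order has to be captured at surgery.

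A reader might also infer that mixing the two drugs must pull their difference toward zero and so favour the trial's rationale. The documents do not support either step. Step 5 shows bias of either sign, and dilution would hide the lower cardiac toxicity expected of ropivacaine.

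**Conclusion.** The concern holds as a limit on what the vital-sign comparison can show. Half of the series (15 of 30) are taken after the other drug and its epinephrine, with no interval stated. Change from a fresh baseline handles stable shifts but not effects still moving within the 5 minutes. Alternation would balance order without removing unequal carry-over, and 4.4 does not confirm that order was alternated.

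The size of the bias cannot be derived from the protocol. A reader might take 92% to 77% of bupivacaine remaining as its size, but that figure rests on an assumed 20 to 60 minute gap, applies only when bupivacaine is given first, and measures drug rather than effect. Likewise, the biases in step 5 show the mechanism and are not estimates. That the first extraction comes before the second injection is inferred from 4.6 and 4.8. The site-specific outcomes, bleeding and side-rated pain, are outside this point.

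**What to change.** - **4.7:** record which drug was injected first in each patient, and state where the second injection falls relative to the first extraction.
- **4.7 and 4.10:** tabulate vital signs by drug and by injection order, as change from that injection's own pre-injection reading. Treat the first-injection contrast (about 8 v 7 if order is balanced) as the uncontaminated between-drug description. Label second-injection readings and events as occurring after both drugs.
- **Summary and 4.4:** reconcile alternation with simple randomization, and say which of them governs injection order.
- **3.1:** state that the vital-sign comparison is descriptive and exploratory.

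The cost is one extra column in the data sheet, a split in the tables, and a more modest vital-sign claim resting on few patients. No treatment or visit changes.

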3.2 SPECIFIC OBJECTIVES

- Measure the amount of intraoperative bleeding (in mL) during procedures performed with 0.5% bupivacaine with 0.2 mL of epinephrine and 0.75% ropivacaine with 0.2 mL of epinephrine.
- Assess potential changes in patients vital signs during and after the administration of local anesthetics.
- Compare the levels of postoperative discomfort associated with anesthetic agents using a visual analog scale (VAS).

JUSTIFICATION

Despite the well-known cardiotoxic and neurotoxic effects of bupivacaine, it continues to be widely used in oral and maxillofacial surgery. This study aims to compare and evaluate the feasibility of using a less toxic anesthetic agent in lower third molar removal surgeries under general anesthesia.

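### A drug difference in intraoperative vital signs is one of three stated aims, but the planned comparison covers only pain and bleeding

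*Protocol*

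**What the plan says.** Protocol section 3.1 sets the general objective as a significant difference between the two anesthetics "in terms of postoperative analgesic capacity, intraoperative hemostasis and the patient's vital signs during the transoperative period". Section 3.2 is softer: "Assess potential changes in patients vital signs during and after the administration of local anesthetics".

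Section 4.7 fixes the data collection, and the schedule applies to both drugs: "Heart rate, blood pressure, and oxygen saturation will be measured and recorded before, immediately after, 1 minute after, and 5 minutes after the injection of". It then states what will be shown: "Significant changes, such as hypo or hypertension, bradycardia or tachycardia, and hypoxia, will be recorded and presented in the results". It names examples but gives no cut-off, reference value or time window.

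Section 4.10 plans the analysis of these data in one sentence: "A descriptive analysis will be performed on the changes in vital signs observed during the operation (if any" is where the description of the vital-sign data ends. The next sentence assigns direct comparison and averages to differences "between the values observed in both the postoperative analgesia evaluation and the transoperative bleeding assessment". Vital signs are not in that sentence.

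The Summary says in general terms that the clinical data from the measurements will be analysed descriptively.

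**The concern.** The trial exists because of bupivacaine's cardiac toxicity (Introduction, section 2.1 and the Justification), so vital signs are not a peripheral domain. An aim framed as a difference between drugs needs an output that sets one drug against the other. For pain and bleeding the protocol names one. For vital signs it names a presentation of significant changes and a description of changes, if any.

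Two things are at stake. First, paired data that could answer the question are collected on every patient and assigned to no comparison. Second, a sentence in the results such as no significant changes were observed could be read as evidence that the drugs behave alike. An event count from 15 patients, with no defined criterion, cannot carry that conclusion.

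**Working it through.** **1. Aim, data and analysis side by side.**

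| Domain | Aim in 3.1 | Output in own section | Compared in 4.10 |
|---|---|---|---|
| Pain | yes | 4.9: values recorded, compared and presented | yes |
| Bleeding | yes | 4.8: values recorded, compared and presented | yes |
| Vital signs | yes | 4.7: significant changes recorded and presented | no |

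Sections 4.8 and 4.9 close with nearly the same sentence. Section 4.7 leaves out the comparison and speaks of significant changes where the others speak of the values.

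**2. Data available.** Inputs from 4.7 and 4.1: 3 signs (blood pressure counted once), 4 times, 2 injections, 15 patients.

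- Per patient: 3 × 4 × 2 = 24 readings.
- Total: 24 × 15 = 360, of which 3 × 1 × 2 × 15 = 90 are pre-injection and 3 × 3 × 2 × 15 = 270 post-injection.
- Possible paired contrasts: 3 signs × 3 post-injection times = 9, each with 15 within-patient pairs.

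None of these is assigned to a between-drug comparison.

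**3. What an empty event list would show.** If no patient is flagged for a drug, the one-sided 95% upper limit p solves (1 − p)^15 = 0.05, so p = 1 − 0.05^(1/15) = 0.181. A true event rate of up to 18% is compatible with 0 of 15.

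**4. How far a count depends on the missing criterion.** The protocol gives no SD, shift or cut-off. The values here are assumptions for illustration and not proposed thresholds.

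- Percent change with SD 10, mean fall of 5 with one drug and 0 with the other, a fall beyond c counted at one time point. Expected counts are 15 × Φ((5 − c)/10) and 15 × Φ(−c/10):
  - c = 10: 4.6 and 2.4
  - c = 15: 2.4 and 1.0
  - c = 20: 1.0 and 0.3
  - c = 30: 0.1 and 0.0
- Percent change with SD 15, no mean shift, changes in either direction counted: 7.6, 2.7 and 0.7 of 15 at cut-offs of 10, 20 and 30.

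The same readings can show a contrast or almost nothing, depending on the criterion.

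**5. Precision of the comparison proposed.** For 15 pairs the 95% half-width is t(14; 0.975)/√15 = 2.145/3.873 = 0.55 SD of the paired differences. If the two injection orders split 8 and 7, the half-widths are 2.365/√8 = 0.84 and 2.447/√7 = 0.92 SD. These are wide, so the result is an estimate and not a confirmatory test.

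**The case against.** The strongest reply is that the protocol does not exclude the missing comparison. All readings are recorded. Section 4.10 speaks of changes without a significance filter, and the Summary promises a descriptive analysis of the clinical data. The sentence on significant changes in 4.7 can be read as an event list on top of the readings. Section 3.2 asks only to assess changes, which a description meets. Cut-offs and table layout are commonly left to a statistical analysis plan, which is not at hand.

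Much of this stands, and it rules out several stronger readings that a reader might infer:

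- *Readings reach the results only if someone flags them.* Neither 4.7 nor 4.10 says so, and the Summary is broader.
- *The assessors know the drug.* The protocol is silent on masking. The unequal volumes in 4.6 (6 mL and 4 mL) make masking harder, but that is inference.
- *The answer depends on who flags a change.* Section 4.7 has the same care team always leading, and the readings are physiological measurements.
- *A real shift would vanish.* If one drug shifts by 0.75 SD with SD 15 (both assumed), the chance that none of 15 is flagged at one time point is below 0.001%, 0.5% and 18% at cut-offs of 10, 20 and 30%. Complete disappearance is unlikely unless the cut-off is high.
- *A quantified loss of power.* The protocol plans no test for vital signs, so a power contrast between two tests would not describe this plan.

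The reply does not remove the mismatch. The general sentence in the Summary names no between-drug comparison, 3.1 asks for one, and 4.10 states which outcomes receive it. An analysis plan that followed 4.10 would inherit the gap.

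**Conclusion.** The point holds as a mismatch between objective and analysis. Section 3.1 makes a between-drug difference in vital signs one of three aims, 4.7 collects paired data suited to it, and 4.10 gives comparison and averages to the other two domains only. This rests on the wording alone and needs no numerical assumption.

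The risk of misreading is secondary but real. The 18% limit depends only on 15 patients with none flagged. The cut-off illustration rests on assumed SDs and an assumed shift, and shows direction, not size.

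The documents do not show that data are suppressed or that assessment is biased. This is a cheap improvement that should be made, not a flaw that invalidates the trial.

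**What to change.** In 4.7 and 4.10, add vital signs to the planned comparison:

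- For all patients, each sign and each scheduled post-injection time, summarise by drug the change from that injection's own pre-injection reading.
- Give the within-patient drug difference in that change with a 95% confidence interval, as an estimate.
- Show the same results by injection order. Both drugs are given in one session, so the second pre-injection reading follows the first drug. The Summary already says that administration is alternated between patients.
- Keep abnormal events as a separate list, derived from the recorded readings by a criterion that the investigators fix before the first surgery. The choice of that criterion is theirs.

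The cost is a change of wording in two sections and one extra table; no new measurement is needed. The downside is at least nine intervals from 15 patients, most of them wide and wider still by order. The text should say that they are descriptive and that an interval including zero does not show the drugs to be equivalent.
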